4.2 Accounting of Subjects

Disposition of the subjects will be summarized. The key contents include number (and percentage) of subjects, number of subjects dosed, median follow-up time, median time on study treatment, the number of subjects who completed study follow-up. In addition, along with reasons, numbers (and percentage) of subjects discontinued treatment and withdrawn from the study will be presented. Listings of these subjects and reasons for discontinuation/withdrawal will be presented

4.3 Demographics and Baseline Characteristics

Demographic data, including age (years), age category (<18, 18-19, 20-29, 30-39, 40-49, 50-55, and >55, also ≤ 35 , > 35), gender, race category, baseline height (cm) and weight (kg) will be summarized.

Baseline data are defined as data collected on the closest date prior to or on the first dosing date. Baseline disease characteristics will be summarized. These include years since disease (MS) onset, years since diagnosis, McDonald criteria, number of relapses in the past 12 months and in the past 3 years, [REDACTED], [REDACTED], baseline MRI, prior MS treatment history, medical history, tobacco use, and status of interferon binding and neutralizing antibodies. Additional variables may be included where applicable.

All demographic and baseline data will be summarized for the full analysis set.

4.4 Study Drug Compliance

Study drug compliance will be summarized, including the total number of injections of daclizumab beta, the percentage of the treatment injections received.

4.5 Concomitant Medications and Non-drug Therapies

Concomitant medication is defined as prescribed or over-the-counter medication used during the study (e.g. either started prior to the study and continued during the study or started after the first dose of study drug). The WHO dictionary will be used for coding concomitant medication. MedDRA is used for coding concomitant non-drug therapies.

Number and percentage of subjects taking concomitant medication and non-drug therapies will be summarized. In addition, number and percentage of subjects taking (switching to) alternative medication will also be summarized.

4.6 General Information on Statistical Analysis

Summary statistics will be generated for all efficacy, safety, PK/PD parameters, demographic/baseline variables and other variables where applicable. For the continuous endpoints, the summary statistics will generally include number of subjects, mean, standard deviation, median, 25th and 75th percentile, minimum and maximum. For categorical endpoints, the summary statistics will generally include number of subjects in corresponding analysis population, number and the percentage of subjects in each category.

In general, all efficacy endpoint analyses where applicable will include the baseline covariates; the covariates included in the statistical models for efficacy endpoints are selected to be consistent with analysis models in other previously reported Phase 3 MS studies.

All statistical tests will be 2-sided with an overall type I error rate of 0.05; no multiple testing adjustment will be performed in this study.

4.7 Protocol Deviations

Protocol deviations identified during site monitoring will be captured in a protocol deviation log and categorized as major or minor deviations. These deviations will be listed.

4.8 Alternative Multiple Sclerosis Medications

In this study, alternative MS medications refers to a list of medications including but not limited to methotrexate, glatimer acetate, mycophenolate mofetil, azathioprine, natalizumab, alemtuzumab, teriflunomide, mitoxantrone, fingolimod, dimethyl fumarate, rituximab, ocrelizumab, laquinimod, and interferon beta throughout this document. Patients who take alternative MS medications during the study will be listed.

5 STATISTICAL ANALYSES

5.1 Primary Analysis

Definition of relapses. Relapses are defined as new or recurrent neurological symptoms not associated with fever or infection, lasting at least 24 hours, and accompanied by new objective neurological findings upon examination by the Examining Neurologist. Protocol-defined relapses up to the end of treatment period visit will be included in the primary analyses. New or recurrent neurological symptoms that occurred less than 30 days following the onset of a protocol-defined relapse will be considered part of the same relapse (i.e., relapses with onset days ≤ 29 days of one another, will be counted as 1 relapse).

Censoring. If a subject prematurely discontinues the treatment and the subject does not experience a protocol-defined relapse prior to discontinuation, the subject will be censored on the last dosing date.

Analysis method. The number of relapses per subject will be summarized. The proportion of subjects who are relapse-free at 6 months will be estimated as 1 minus the cumulative

probability of relapses from the Kaplan-Meier product limit method. The time to relapse is the number of days from the first dosing date to the date of first relapse, or end of treatment period, whichever comes first. Time to first relapse will be summarized by 10th, 25th and 50th percentile.

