### **7.2. Overall Study Duration and Follow-Up**

The study will consist of a 28-day (+3 days) screening period for each subject, a 12-month treatment period, and a 4-month remote safety follow-up visit after the subject's last treatment injection. The end of the study for each subject will be the last study visit or the visit at which the subject discontinues from the study (before the 12-month visit). Each follow-up visit will include a 4-day window before and after the visit for completion of all assessments. The follow-up period will include efficacy and safety following treatment initiation of daclizumab. The end of the study overall will be defined as the end of the 12-month study follow-up period for the last patient. The 4-month safety follow-up visit will be conducted remotely after the 12-month study follow-up visits have been completed.

Subjects having tentative disability progression identified near the end of the core study (e.g., Month 12) will attend additional follow-up visits 12 and 24 weeks later to confirm progression.

Subjects may discontinue treatment at any time during the study, and they will be followed for an additional 4 months to collect data on safety, LFT, MS treatment, relapses, and the use of concomitant medications.

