### **13.4. Primary Endpoint Analysis**

#### **13.4.1. Efficacy Analysis**

The proportion of subjects relapse-free at Month 6 will be estimated using the Kaplan-Meier approach. This will be calculated as 1 minus the proportion of subjects with relapses at Month 6.

CONFIDENTIAL

The information contained herein may not be used, disclosed, or published without the written consent of  
Biogen MA Inc.

For the Kaplan-Meier approach, the time to relapse is the number of days from the date of the first dose of daclizumab to the date of first relapse, or end of study, whichever comes first. The Cox proportional hazard model will be used to estimate the hazard ratio of relapses within subject subgroups of interest. The subgroups of interest will be defined in the SAP.

The proportion of subjects relapse-free 6 months before and 6 months after switching to daclizumab will be compared using McNemar's Test for subjects who had relapse information available at the above time points.

For primary endpoints, sensitivity analyses will be performed on the ITT population excluding those patients who missed 2 or more consecutive doses within 6 months. Additional details regarding the sensitivity analysis will be described in the SAP.

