4.1 Treatment Period Definitions

Based on the schedule of assessment, we have the following definitions:

- **the first dosing date** is the date when the subject is first dosed;
- **the last dosing date** is the date of the last date the subject is dosed;
- **The end of study date** is the last visit date;

- **Treatment period, or, time on (study) treatment**, is defined as the time between the first dosing date and the last dosing date; it is calculated as the last dosing date minus the first dosing date + 1; also known as the time exposed to study drug;
- **Time on study, or study period**, is defined as the time between the first dosing date and the end of study date, calculated as the last visit date – the first dosing date + 1.

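### SAP 5.1 gives inconsistent end dates for the primary Kaplan-Meier analysis: relapses count up to an undefined visit, while event-free time stops at the last dose

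*SAP*

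**What the plan says.** SAP 5.1 has three sentences that set the end of observation for the primary endpoint.

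- **Which relapses count:** "Protocol-defined relapses up to the end of treatment period visit will be included in the primary analyses".
- **Censoring of early stoppers:** if "the subject does not experience a protocol-defined relapse prior to discontinuation, the subject will be censored on the last dosing date".
- **The time variable:** days from the "first dosing date to the date of first relapse, or end of treatment period, whichever comes first".

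SAP 4.1 says that the treatment period "is defined as the time between the first dosing date and the last dosing date", so the second and third sentences both point to the last dose. The visit in the first sentence is not defined in SAP 4.1 and is not a visit title in Protocol Table 1. SAP 4.1 defines first-dose, last-dose and end-of-study dates, but no discontinuation date.

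Protocol 13.4.1 uses a different end: time from the first dose "to the date of first relapse, or end of study, whichever comes first". Protocol 7.2 sets that end for each subject: "The end of the study for each subject will be the last study visit or the visit at which the subject discontinues". SAP 2 and 4 explain the early termination and say that some endpoints are dropped or only listed. They do not mention a change to the end date of the primary analysis.

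**The concern.** A Kaplan-Meier estimate needs one rule for leaving the risk set, applied equally to those who relapse and those who do not. Dosing is monthly, so a visit that closes treatment will normally fall some days or weeks after the last injection. A relapse in that gap is included by the first sentence and cut off by the third. If it is included while event-free subjects leave at their last dose, the numerator covers time that the denominator does not, and the relapse-free proportion is too low.

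Only subjects whose last dose precedes Month 6 can move the primary estimate. In a study that ran its course these might be few. Here SAP 2 reports that drug supply stopped and the study was terminated, so many such subjects are foreseeable. The programmer has to choose between the sentences, and the same data can then give different primary results.

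**Working it through.** **1. The plan's own figure.** Protocol 13.1 gives 95% confidence half-widths of 8.3 and 6.7 points for 80% and 88% with 90 evaluable subjects. The formula 1.96 × √(p(1−p)/n) gives 1.96 × √(0.80 × 0.20/90) = 8.26 points and 1.96 × √(0.88 × 0.12/90) = 6.71 points, so both reproduce. With the roughly 30 subjects of SAP 4, the same formula gives 14.3 and 11.6 points.

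**2. One data set, three readings (invented data).** Take 30 subjects. Three relapse on treatment, on days 30, 60 and 150. Fifteen have their last dose on day 91, and one of these relapses on day 110, before a visit on day 120. Twelve are event-free past Month 6. After day 60 the estimate is 28/30 under every reading.

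| Reading | Remaining factors | Month 6 estimate |
|---|---|---|
| Relapses to the visit, event-free subjects censored at last dose | 13/14 × 12/13 | 80.0% |
| Both to the visit | 27/28 × 12/13 | 83.1% |
| Both to the last dose | 12/13 | 86.2% |

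The gap relapse was placed by hand. The table shows that the sentences disagree, not how large the effect is likely to be.

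**3. Expected size.** The inputs from the documents are monthly doses from baseline to Month 11 (Protocol Table 1, note 8) and Month 6 proportions of 80% and 88% (Protocol 13.1). The following are assumptions:

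- constant relapse hazard, −ln(0.80)/6 = 0.0372 or −ln(0.88)/6 = 0.0213 per month;
- supply stop uniform over 12 months from first dose, with 9 and 18 months as the range;
- 10% per year stopping for other reasons;
- stopping unrelated to relapse;
- the closing visit falls on the stop date.

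The share with a last dose before Month 6 is 1 − P(supply stop after Month 6) × 0.9^0.5. For 12 months this is 1 − (6/12) × 0.949 = 53%. For 9 months it is 1 − (3/9) × 0.949 = 68%, and for 18 months 1 − (12/18) × 0.949 = 37%.

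Simulation with 1,000,000 subjects per scenario, accurate to about 0.1 to 0.2 points, compared two rules:

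| Supply stop over | Last dose before Month 6 | Relapses to visit, censoring at last dose: true 80% / true 88% | Both at last dose |
|---|---|---|---|
| 9 months | 68% | 78.1% / 86.9% | 80% / 88% |
| 12 months | 53% | about 79% / about 87% | 80% / 88% |
| 18 months | 37% | 79.3% / 87.6% | 80% / 88% |

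The downward bias of the mixed rule is 0.7 to 1.9 points at 80% and 0.4 to 1.1 points at 88%. Ending both events and censoring at the visit also recovers the true value.

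**4. Dependence on the gap.** In a separate simulation, the mean gap from last dose to visit was set to 14, 30 or 60 days. Over true values of 80% and 88%, the mixed rule lost 0.1 to 0.5 points with 10% stopping before Month 6, 0.6 to 3.5 points with 50%, and 1.2 to 6.5 points with 70%. The undefined visit therefore drives the size.

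**5. A 30-subject study.** Under the 12-month assumption, the last-dose and visit rules differ by at least 3 points in about 16% of studies (true 80%) and 11% (true 88%). The median difference is 1.1 and 0.6 points. The standard deviation of the estimate is about 9 and 7 points.

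**The case against.** The best defence is that two of the three sentences agree. The time variable ends at the last dose by definition, and the only stopping-related treatment date in SAP 4.1 is the last dosing date. If *discontinuation* means that date, the Censoring sentence treats events and event-free time alike and the inclusion sentence is merely loose wording. On-treatment censoring is legitimate, the study-period relapse rate in SAP 5.2.2 keeps later relapses visible, and with about 30 subjects the sampling error is larger than the effect.

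Much of this stands. The Censoring sentence on its own is asymmetric only if discontinuation is later than the last dose, and the SAP does not settle that. But the inclusion sentence still conflicts with the last-dose cut-off under either reading, and the study-period rate does not correct the Month 6 proportion.

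A reader might go further and infer that the last-dose rule is biased upward, because dosing is held after a suspected relapse (Protocol 10.5) and late doses are skipped (Protocol 10.2), so that relapses fall after the last dose. The documents do not support this. Protocol 10.5 asks for contact within 48 hours and evaluation within 72 hours, at most about 5 days in sequence, and Protocol 10.2 skips only a dose more than 2 weeks late. With a 5-day hold in the model of step 3, about 0.1 to 0.2% of relapsers before Month 6 lose their next dose, and the last-dose estimate stays at 80.0% and 88.0%. Any larger share of relapsers who receive no further dose would be purely assumed.

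**Conclusion.** SAP 5.1 does not give one end date for the primary analysis. Following its inclusion and censoring sentences together, with the visit after the last dose, biases the Month 6 proportion downward by about 0.4 to 1.9 points. This rests on the assumed supply-stop timing and constant hazard; the documents give no follow-up distribution. The size is smaller if few subjects stop before Month 6 and larger if the visit comes later.

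Ending both events and censoring at the last dose is unbiased when stopping is unrelated to relapse. Its faults are that it discards observed follow-up and replaces the Protocol's end of study without saying so. No decision depends on this point, since there is no success threshold and sampling error dominates. It remains an avoidable ambiguity, and under one natural reading a wrong rule, in the primary result of the abbreviated report.

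**What to change.** In SAP 5.1, state one end date, defined in SAP 4.1, and apply it to both events and censoring. Define or delete the *end of treatment period visit*, and define *discontinuation*. Then choose one of two:

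- **End of study as primary**, per subject, as in Protocol 13.4.1 and 7.2. Say whether it includes the remote safety visit. SAP 4.1 uses the last visit date without saying so, and Protocol 7.2 places that visit outside the 12-month follow-up: "The 4-month safety follow-up visit will be conducted remotely after the 12-month study follow-up visits have been completed". This matters because a relapse under SAP 5.1 must be "accompanied by new objective neurological findings upon examination by the Examining Neurologist", and Table 1 marks a relapse assessment but no physical examination at that visit.
- **An on-treatment end date as primary**, stated as a change from Protocol 13.4.1 with the reason.

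Report the other as a sensitivity analysis.

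The cost is SAP wording and reprogramming; no new data are needed. The real downside of end of study is that it brings in some off-drug follow-up, possibly on alternative MS medication. Reporting both analyses shows how much that matters.

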5.2 Secondary Analysis

Due to the early termination of the study, the permanent discontinuation rate of daclizumab is not analyzed.

5.2.1 Analysis for the proportion of subjects experiencing relapse requiring hospitalization and/or steroid treatment at Month 12

Relapses requiring hospitalization and/or steroid treatment will be listed by subject with relapse evaluation date and onset date.

5.2.2 Analysis for Annualized Relapse Rate (ARR)

ARR will be analyzed for both treatment period and study period. Please see section 4.1 for their definitions.

The number of relapses observed during the treatment period (or during the study period) will be summarized as a categorical variable (number of relapse being 0, 1, 2, 3 and ≥ 4).

The unadjusted relapse rate will be calculated as the total number of relapses observed divided by the total number of days on treatment (or on study) multiplied by 365.25.

If there is sufficient data, the adjusted mean annualized relapse rate and its 95% confidence interval (CI) during the treatment period will be estimated by a negative binomial model; proper covariates are adjusted in the model. The logarithmic transformation of the number of days in the study will be included in the model as the “offset” parameter. If the data is under-dispersed or if the negative binomial regression model does not converge, a Poisson model will be used instead of the negative binomial regression model. Dispersion will be evaluated from the Pearson Chi-Square statistic. If the ratio of the Pearson Chi-Square statistic to the degrees of freedom is < 1 then a Poisson regression model will be used.

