### **13.5. Secondary Endpoints Analysis**

#### **13.5.1. Efficacy Analysis**

The proportion of subjects relapse-free at Month 12 will be estimated using Kaplan-Meier approach. This will be calculated as 1 minus the proportion of subjects with relapses at Month 12. For the Kaplan Meier approach, the time to relapse is the number of days from the date of the first dose of daclizumab to the date of first relapse, or end of study, whichever comes first. The Cox proportional hazard model will be used to estimate the hazard ratio of relapses between subject subgroups of interest.

The proportion of subjects relapse-free 12 months before and 12 months after switching to daclizumab will be compared using McNemar's Test for subjects who had relapse information available at the above time points (study completers).

The proportion of subjects experiencing relapse requiring hospitalization and/or steroid treatment at Month 12 will be estimated using the Kaplan-Meier approach. For the Kaplan-Meier approach, the time to relapse requiring hospitalization and/or steroid treatment will be the number of days from the date of the first dose of daclizumab to the date of first relapse requiring hospitalization and/or steroids treatment, or end of study, whichever comes first. A Cox proportional hazard model will be used to estimate the hazard ratio of relapses requiring hospitalization and/or steroids treatment between subject subgroups of interest.

The ARR with 95% CI at Month 12 (calculated as the total number of relapses divided by the total number of person-years in the study at the end of Month 12 for each subject) will be estimated using a negative binomial model. If the data are under-dispersed or if the negative binomial regression does not converge, a Poisson regression model with the same covariates will be used instead. Given that subjects may have more than 1 relapse in 12 months, the number of relapses will be summarized both as a continuous variable and as a categorical variable.

The number of new Gd+ enhanced and T1 hypointense lesions at Month 6 and Month 12 and the number of new or newly enlarged T2 hyperintense lesions at Month 6 and Month 12 when compared with baseline will be summarized both as continuous variables and as categorical variables. A negative binomial model adjusting for the corresponding baseline MRI lesion counts will be used to estimate the adjusted mean and lesion mean ratio between subject subgroups of interest.

CONFIDENTIAL

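### The SAP's study-period ARR runs past Month 12 to a remote contact with no scheduled examination to confirm a relapse

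*SAP*

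**What the plan says.** SAP 5.2.2 says that "ARR will be analyzed for both treatment period and study period". The unadjusted rate is the "total number of relapses observed divided by the total number of days on treatment (or on study) multiplied by 365.25". In SAP 4.1 the study period "is defined as the time between the first dosing date and the end of study date", and the end of study date "is the last visit date", with no restriction to clinic visits.

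Table 1 of the protocol numbers the safety follow-up as Visit 9, at Month 15. It marks a relapse assessment there but no physical examination. On its mode and timing, Protocol 7.2 says: "The 4-month safety follow-up visit will be conducted remotely after the 12-month study follow-up visits have been completed".

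The SAP's only relapse definition, in 5.1, requires that symptoms be "accompanied by new objective neurological findings upon examination by the Examining Neurologist".

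Protocol 13.5.1 bases the ARR on the "total number of person-years in the study at the end of Month 12 for each subject", and SAP 1.2 still names the endpoint as the ARR at Month 12. SAP 5.2.2 sets no such limit. Its adjusted model estimates the ARR for the treatment period, but takes the logarithm of days in the study as offset.

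**The concern.** A rate needs events and person-time gathered under the same rule. Here the denominator runs to a remote contact, while the numerator depends on an examination that is not scheduled in the last part of that time. Relapses in the interval may therefore be under-confirmed while every day of it counts.

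Even with complete confirmation, the rate would cover months off study drug and after Month 12, possibly on another MS therapy. SAP 4.8 lists such therapies but states no censoring for ARR. The result is then not the endpoint that the protocol defines.

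Early termination makes this more important. The abbreviated report will draw on data available at withdrawal plus the safety follow-up (SAP section 2), so the 4 months after the last dose may be a large part of many subjects' time.

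**Working it through.** **Inputs.** Last planned dose at Month 11 (Table 1, note 8). Safety contact 4 months after the last dose (Protocol 4.2). Visit windows of ±4 days at Month 12 and ±14 days at Month 15 (Table 1). Illustrative ARR of 0.22, from the active-controlled phase 3 trial cited in Protocol 5.1.4. One month is taken as 30.4375 days.

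**1. The plan's own timeline.** 11 + 4 = Month 15, as in Table 1. Screening of 28 to 31 days plus 15 months gives 15.9 to 16.0 months, which agrees with the stated maximum of 16 months. The documents give no figure for the remote share of ARR time.

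**2. Completer.** Share after the last scheduled clinic visit = (15 − 12)/15 = 20.0%. With visit windows:
- shortest: (442.6 − 369.3)/442.6 = 16.6%
- longest: (470.6 − 361.3)/470.6 = 23.2%

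**3. Early stopper who has the remote contact.** With the last dose at Month k and the last clinic visit d months later (d is an assumption), share = (4 − d)/(k + 4).

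| Last dose | d = 0 | d = 1 | d = 2 |
|---|---|---|---|
| Month 3 | 57.1% | 42.9% | 28.6% |
| Month 6 | 40.0% | 30.0% | 20.0% |
| Month 9 | 30.8% | 23.1% | 15.4% |

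**4. Not everyone has the remote contact.** The share is 0% for a subject whose last visit is in clinic. If a fraction q of completers has the contact, the pooled share is 3q/(12 + 3q): 15.8% at q = 0.75 and 11.1% at q = 0.5. Both values of q are assumptions.

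**5. Effect on the rate, completers.** Assume a constant true rate, with a fraction f of relapses in the 3-month interval confirmed. The reported rate is then 0.22 × (12 + 3f)/15.
- f = 0: 0.22 × 0.80 = 0.176
- f = 0.5: 0.22 × 0.90 = 0.198
- f = 1: 0.22, no undercount

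**6. The adjusted model.** If treatment-period relapses are set against days in the study, a completer's 11 months of treatment are replaced by 15 months. The factor is 11/15 = 0.73, whatever the value of f.

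**The case against.** The strongest reply is that examination does not stop at Month 12. Protocol 10.5 calls for the Study Neurologist to evaluate a suspected relapse within 72 hours, outside the visit schedule. Protocol 7.2 collects relapses for 4 months after treatment stops, and Table 1 marks a relapse assessment at Visit 9. This stands in part: what is missing is a scheduled examination, not every examination. Protocol 10.5 comes under treatment schedule modification, however, and its reach after the last dose is unclear.

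Physical examinations at Months 3, 6, 9 and 12 are also 3 months apart, so the contrast with earlier follow-up is one of degree. Still, a relapse before Month 12 is followed by a scheduled clinic assessment; one after Month 12 is not.

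SAP 5.2.2 refers only to relapses observed, and the definition in Protocol 11.2.2.4 needs no examination findings. Under that definition a remote report could count. But SAP 5.1 holds the only definition in the SAP, and the missing Month 12 limit would remain either way.

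Protocol 7.2 also says: "The end of the study overall will be defined as the end of the 12-month study follow-up period for the last patient". One could take this to exclude Visit 9. The SAP's end date is nevertheless the last visit, and the protocol calls the remote contact a visit throughout.

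Finally, the study-period ARR is a labelled addition to the treatment-period ARR. The unadjusted treatment-period figure ends at the last dose and is untouched. That is correct, but it does not extend to the adjusted model.

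**Conclusion.** The concern holds. On a plain reading, the SAP lets about 20% of a nominal completer's study-period days into the denominator with no scheduled examination to confirm a relapse, and beyond the Month 12 endpoint. For early stoppers who have the remote contact the share is usually larger. If nothing in that interval is confirmed, the completers' ARR is understated by a fifth. If everything is confirmed, there is no undercount, but time off study drug after Month 12 is still included. The adjusted treatment-period model takes in the same end date through its offset.

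Three stronger readings are tempting, and the documents do not support them:
- A reader might infer that relapses in the remote interval cannot count. Protocol 7.2 and 10.5 and the Visit 9 assessment leave room for confirmation.
- A reader might take 20% as a minimum. Visit windows alone allow 16.6%, and the share is 0% when the last visit is in clinic.
- A reader might conclude that the rate must come out too low. If relapses are captured and are more frequent off drug, it could rise.

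The sizes rest on the assumed last clinic date for early stoppers, the assumed fraction confirmed and a constant relapse rate. The endpoint is secondary, in a terminated study of about 30 subjects. The change is worth making but does not threaten the primary analysis.

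**What to change.** In SAP 4.1 and 5.2.2:

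- For ARR, end the study period at the earlier of Month 12 and the last scheduled in-clinic or early-discontinuation visit with a relapse assessment. Do not let a relapse-triggered unscheduled visit set this date: it would lengthen follow-up only for subjects who relapse, so person-time would depend on the event.
- Report relapses and person-time after that date separately, marking each relapse as examined or not examined.
- Use the logarithm of days on treatment as the offset in the treatment-period model.
- State that Visit 9 can be the end of study date for safety, and keep the last-visit definition there.

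The cost is SAP wording, one derived date and a changed offset. No new data are needed. The ARR would rest on slightly less person-time and might look slightly less favourable.
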